8.2.9. Tuberculosis Evaluations

8.2.9.1. Initial Tuberculosis Evaluation

Participants must undergo testing for TB (refer to Section 10.2, Appendix 2: Clinical Laboratory Tests and their medical history assessment must include specific questions about a history of TB or known occupational or other personal exposure to individuals with active TB. The participant should be asked about past testing for TB, including chest radiograph results and responses to tuberculin skin or other TB testing. Investigators have the option to use both the QuantiFERON-TB (or T-SPOT® for sites in Japan) test and the tuberculin skin test to screen for latent TB if they believe, based on their judgement, that the use of both tests is clinically indicated to evaluate a participant who is high risk of having latent TB. If either the QuantiFERON-TB (or T-SPOT for sites in Japan) test or the tuberculin skin test is positive, the participant is considered to have latent TB infection for the purposes of eligibility for this study.

Participants with a negative QuantiFERON-TB (or T-SPOT for sites in Japan) test result (and a negative tuberculin skin test result in countries in which the QuantiFERON-TB test is not approved/registered or the tuberculin skin is mandated by local health authorities) are eligible to continue with pre-randomization procedures. Participants with a newly identified positive QuantiFERON-TB (or T-SPOT for sites in Japan or tuberculin skin) test result must undergo an evaluation to rule out active TB and initiate appropriate treatment for latent TB. Appropriate treatment for latent TB is defined according to local country guidelines for immunocompromised participants. If no local country guidelines for immunocompromised participants exist, US guidelines should be followed, or the participant will be excluded from the study.

A participant whose first QuantiFERON-TB test result is indeterminate should have the test repeated. In the event that the second QuantiFERON-TB test result is also indeterminate, the participant may be enrolled without treatment for latent TB if active TB is ruled out, their chest radiograph shows no abnormality suggestive of TB (active or old, inactive TB) and the participant has no additional risk factors for TB as determined by the investigator. For sites in Japan, a participant whose first T-SPOT test result is borderline should have the test repeated. In the event that the second T-SPOT (for sites in Japan) test result is also borderline, the participant may be enrolled without treatment for latent TB if active TB is ruled out, their chest radiograph shows no abnormality suggestive of TB (active or old, inactive TB) and the participant has no additional risk factors for TB as determined by the investigator. This determination must be promptly reported to the medical monitor or designee and recorded in the participant's source documents and initialed by the investigator.

8.2.9.2. Ongoing Tuberculosis Evaluation

Early Detection of Active Tuberculosis

To aid in the early detection of TB reactivation or new TB infection during study participation, participants must be evaluated for signs and symptoms of active TB at scheduled visits (refer to the SoA [Section 1.3]). The following series of questions is suggested for use during the evaluation:

- “Have you had a new cough of >14 days’ duration or a change in a chronic cough?”
- “Have you had any of the following symptoms:
 - Persistent fever?
 - Unintentional weight loss?
 - Night sweats?”
- “Have you had close contact with an individual with active TB?” (If there is uncertainty as to whether a contact should be considered “close,” a physician specializing in TB should be consulted.)

If the evaluation raises suspicion that a participant may have TB reactivation or new TB infection, an immediate and thorough investigation should be undertaken, including, where possible, consultation with a physician specializing in TB.

Investigators should be aware that TB reactivation in immunocompromised participants may present as disseminated disease or with extrapulmonary features. Participants with evidence of active TB should be referred for appropriate treatment.

Participants who experience close contact with an individual with active TB during the conduct of the study must have a repeat chest radiograph, a repeat QuantiFERON-TB (or T-SPOT for sites in Japan) test, a repeat tuberculin skin test in countries in which the QuantiFERON-TB test is not approved/registered or the tuberculin skin test is mandated by local health authorities, and, if possible, referral to a physician specializing in TB to determine the participant’s risk of developing active TB and whether treatment is warranted. Study intervention administration should be interrupted during the investigation. A positive QuantiFERON-TB (or T-SPOT for sites in Japan) test or tuberculin skin test result should be considered detection of latent TB. Participants with a newly identified positive QuantiFERON-TB (or T-SPOT for sites in Japan or tuberculin skin) test result must undergo an evaluation to rule out active TB and initiate appropriate treatment for latent TB. Appropriate treatment for latent TB is defined according to local country guidelines for immunocompromised participants. If no local country guidelines for immunocompromised participants exist, US guidelines should be followed, or the participant will be excluded from the study. If the QuantiFERON-TB test result is indeterminate, the test should be repeated. For sites in Japan, a participant whose first T-SPOT test result is borderline should have the test repeated. Participants should be encouraged to return for all subsequent scheduled study visits according to the protocol. Participants who discontinue treatment for latent TB prematurely or who are noncompliant with therapy must immediately discontinue further administration of study

intervention and be encouraged to return for all subsequent scheduled study visits according to the SoA (Section 1.3).

8.3. Adverse Events, Serious Adverse Events, and Other Safety Reporting

Timely, accurate, and complete reporting and analysis of safety information, including AEs, serious AEs, and product quality complaint (PQC), from clinical studies are crucial for the protection of participants, investigators, and the sponsor, and are mandated by regulatory agencies worldwide. The sponsor has established Standard Operating Procedures in conformity with regulatory requirements worldwide to ensure appropriate reporting of safety information; all clinical studies conducted by the sponsor or its affiliates will be conducted in accordance with those procedures.

Adverse events will be reported by the participant (or, when appropriate, by a caregiver, or surrogate) for the duration of the study.

Further details on AEs, SAEs, and PQC can be found in Section 10.4, Appendix 4: Adverse Events, Serious Adverse Events, Product Quality Complaints, and Other Safety Reporting: Definitions and Procedures for Recording, Evaluating, Follow-Up, and Reporting.

8.3.1. Time Period and Frequency for Collecting Adverse Event and Serious Adverse Event Information

All Adverse Events

All AEs and special reporting situations, whether serious or non-serious, will be reported from the time a signed and dated ICF is obtained until completion of the participant's last study-related procedure, which may include contact for follow-up of safety.

Serious Adverse Events

All SAEs, as well as PQC, occurring during the study must be reported to the appropriate sponsor contact person by study site personnel within 24 hours of their knowledge of the event.

Serious adverse events, including those spontaneously reported to the investigator within 12 weeks after the last dose of study intervention, must be reported. The sponsor will evaluate any safety information that is spontaneously reported by an investigator beyond the time frame specified in the protocol.

Information regarding serious adverse events will be transmitted to the sponsor using the Serious Adverse Event Form and Safety Report Form of the eCRF, which must be completed and reviewed by a physician from the study site and transmitted to the sponsor within 24 hours. The initial and follow-up reports of a serious adverse event should be transmitted electronically or by facsimile (fax). Telephone reporting should be the exception and the reporter should be asked to complete the appropriate form(s) first.

8.3.2. Method of Detecting Adverse Events and Serious Adverse Events

Care will be taken not to introduce bias when detecting adverse events or serious adverse events. Open-ended and nonleading verbal questioning of the participant is the preferred method to inquire about AE occurrence.

Solicited Adverse Events

Solicited AEs are predefined local at the infusion site and systemic events for which the participant is specifically questioned and which are noted by participants in their diary (see Section 8. Study Assessments and Procedures).

Unsolicited Adverse Events

Unsolicited AEs are all AEs for which the participant is not specifically questioned in the participant diary.

8.3.3. Follow-up of Adverse Events and Serious Adverse Events

The investigator is obligated to perform or arrange for the conduct of supplemental measurements and evaluations as medically indicated to elucidate the nature and causality of the AE, SAE, or PQC as fully as possible. This may include additional laboratory tests or investigations, histopathological examinations, or consultation with other health care professionals.

Adverse events, including pregnancy, will be followed by the investigator as specified in Section 10.4, Appendix 4: Adverse Events, Serious Adverse Events, Product Quality Complaints, and Other Safety Reporting: Definitions and Procedures for Recording, Evaluating, Follow-up, and Reporting.

8.3.4. Regulatory Reporting Requirements for Serious Adverse Events and Anticipated Events

The sponsor assumes responsibility for appropriate reporting of AEs to the regulatory authorities. The sponsor will also report to the investigator (and the head of the investigational institute where required) all suspected unexpected serious adverse reactions (SUSARs). The investigator (or sponsor where required) must report SUSARs to the appropriate Independent Ethics Committee/Institutional Review Board (IEC/IRB) that approved the protocol unless otherwise required and documented by the IEC/IRB. A SUSAR will be reported to regulatory authorities unblinded. Participating investigators and IEC/IRB will receive a blinded SUSAR summary, unless otherwise specified.

An anticipated event is an AE that commonly occurs in the study population independent of exposure to the drug under investigation. For the purposes of this study the following SAEs will be considered anticipated events: No anticipated events have been identified for this study.

These anticipated events will be periodically analyzed in aggregate by the sponsor during study conduct. The sponsor will prepare a safety report in narrative format if the aggregate analysis indicates that the anticipated event occurs more frequently in the intervention group than in the control group and the sponsor concludes there is a reasonable possibility that the drug under investigation caused the anticipated event.

The plan for monitoring and analyzing the anticipated events is specified in a separate Anticipated Events Safety Monitoring Plan. The assessment of causality will be made by the sponsor's unblinded safety assessment committee.

The sponsor assumes responsibility for appropriate reporting of the listed anticipated events according to the requirements of the countries in which the studies are conducted.

8.3.5. Pregnancy

All initial reports of pregnancy in female participants or partners of male participants must be reported to the sponsor by the study site personnel within 24 hours of their knowledge of the event using the appropriate pregnancy notification form. Abnormal pregnancy outcomes (eg, spontaneous abortion, fetal death, stillbirth, congenital anomalies, ectopic pregnancy) are considered SAEs and must be reported using the Serious Adverse Event form.

Any participant who becomes pregnant during the study must discontinue further study intervention (see Section 7.1, Discontinuation of Study Intervention).

Follow-up information regarding the outcome of the pregnancy and any postnatal sequelae in the infant will be required.

8.3.6. Adverse Events of Special Interest

Any newly identified malignancy or case of active TB occurring after the first study intervention administration(s) in participants participating in this clinical study must be reported by the investigator according to the procedures in Section 10.4, Appendix 4: Adverse Events, Serious Adverse Events, Product Quality Complaints, and Other Safety Reporting: Definitions and Procedures for Recording, Evaluating, Follow-Up, and Reporting. Investigators are also advised that active TB is considered a reportable disease in most countries. These events are to be considered serious only if they meet the definition of an SAE.

8.4. Pharmacokinetics and Immunogenicity

Venous blood samples will be collected for the measurement of serum bermekimab concentrations and detection of antibodies to bermekimab at the time points presented in the SoA (Section 1.3).

At visits in which serum bermekimab concentration and/or antibodies to bermekimab will be evaluated, 1 venous blood sample of sufficient volume should be collected, and each serum sample should be divided into 3 aliquots: 1 for serum concentration of bermekimab, 1 for antibodies to bermekimab, and 1 back-up.

Serum samples will also be collected at the final visit from participants who terminate study participation/intervention early. Blood samples collected for serum bermekimab concentrations and/or antibodies to bermekimab may also be used for exploratory biomarker analyses.

A random venous blood sample for population PK analysis will be collected from the first 20 participants of the study on any day between Weeks 2 to 12, except on the days of the scheduled study visits. If possible, we would like to encourage obtaining this sample between Week 2 and Week 6, although if it is done after Week 6, it would not constitute a protocol deviation. Additionally, this blood sample must be collected at least 24 hours prior to or after the actual time

of study intervention administration. All the remaining participants (last 20 participants of Part B, and all 20 participants of Part C) may choose to also participate in the collection of this population PK sample as optional. Each population PK serum sample will be divided into 2 aliquots: 1 for serum concentration of bermekimab and a back-up.

The exact dates and times of blood sample collection must be recorded in the laboratory requisition form. See the laboratory manual for further information regarding collection, handling, and shipment of biological samples. Genetic analyses will not be performed on these serum samples. Participant confidentiality will be maintained.

Pharmacokinetic Analytical Procedures

Serum samples will be analyzed to determine serum bermekimab concentrations using a validated, specific, and sensitive immunoassay method by or under the supervision of the sponsor. The sponsor, or its designee, under conditions in which the participants' identity remains blinded, will assay these samples.

Immunogenicity Analytical Procedures

The detection and characterization of antibodies to bermekimab will be performed using a validated immunoassay method by or under the supervision of the sponsor. Serum samples will be screened for antibodies binding to bermekimab and the titer of confirmed positive samples will be reported. Antibodies to bermekimab may be further characterized and/or evaluated for their ability to neutralize the activity of bermekimab.

8.5. Pharmacogenomics

Genetic variation can be an important contributory factor to interindividual differences in drug disposition and response and may also serve as a marker for disease susceptibility and prognosis. Here, pharmacogenomic research refers to the analysis of 1 or more candidate genes or of the analysis of markers throughout the genome in relation to bermekimab and AD clinical endpoints. The goal of the pharmacogenomic research component is to explore factors that may influence the PK, PD, efficacy, or tolerability of bermekimab and to evaluate genetic factors previously reported to be associated with AD or to identify new associations with disease. These DNA samples may be used to help address emerging issues and to enable the development of safer, more effective, and more precisely applied therapies.

A pharmacogenomic whole blood sample will be collected to allow for pharmacogenomic research, as necessary (where local regulations permit). Participation in the pharmacogenomic research is optional.

Genotyping or sequencing techniques will be used to assess variation in the filaggrin gene, a risk factor for AD, and interleukin-1 alpha gene (*IL1A*), the target of bermekimab. Additionally, genome-wide genotyping or sequencing will be used to assess variation genome-wide.

8.6. Biomarkers

Biomarker samples will be collected to evaluate the PD and mechanism of action of bermekimab or help to explain interindividual variability in clinical outcomes or may help to identify population subgroups that respond differently to the intervention.

The goal of the biomarker analyses is to evaluate the PD of bermekimab and aid in evaluating the intervention-clinical response relationship.

Biomarker assessment will include the evaluation of relevant markers in serum, blood, skin biopsies, and tape strips for all participants. The samples will be used to better understand the biology of AD; to provide biological assessment of the response of participants to treatment with bermekimab; to analyze differences between responders and nonresponders; and to determine if the markers can be used to classify participants as potential responders prior to treatment. Blood samples will be separated into serum and peripheral blood mononuclear cells (PBMCs) for biomarker analysis. Samples for serum biomarkers, flow cytometry and gene expression from blood will be collected at time points according to the SoA. Instructions for the collection and shipment of these samples are found in the Laboratory Reference Manual and Biopsy Collection Manual.

8.6.1. Skin Biomarkers

Non-invasive skin sampling through tape stripping is mandatory and will be collected from all participants at time points specified in the SoA. At baseline, tape strips will be collected from both lesional and adjacent non-lesional areas; at Weeks 4, and 16, only lesional areas will be sampled. Tape stripping allows for the measurement of gene expression as well as levels of proteins or other biomarkers in the stratum corneum.

Skin biopsy samples will be collected from all participants of the study at time points specified in the SoA. At the baseline sampling time point (Week 0), biopsy samples will be collected from both lesional and adjacent non-lesional areas; at Week 6 or 16, two lesional areas will be sampled. Gene expression analysis of skin biopsy samples will be performed to investigate differential gene expression during treatment compared with baseline to explore PD, mechanism of action, and differences in responders vs nonresponders. At Week 6 or 16, a whole biopsy will be dedicated for proteomic analysis. In addition, the tissue biopsies may be analyzed for histological readouts and immunohistochemistry to explore the effects of study intervention on cellular composition and PK/PD within skin tissue.

8.6.2. Serum Biomarkers

Serum samples will be collected from all participants at time points specified in the SoA (Section 1.3). Potential circulating factors to be evaluated may include cytokines and other inflammatory markers (eg, CCL17/TARC), and other categories of biomarkers potentially associated with AD or related to the mechanism of action of bermekimab.

8.6.3. Flow Cytometry Analysis

Whole blood samples will be collected from all participants at time points specified in the SoA (Section 1.3), and PBMC will be isolated. Flow cytometry analysis of blood cell samples will be

utilized to monitor the effects of bermekimab on circulating immune cell populations. Cell surface markers such as, but not limited to, those for T cell subsets (eg, Th1, Th2), dendritic cells (DCs), and B cells will be assessed.

8.6.4. Gene Expression Analysis in Whole Blood

Whole blood samples will be collected from all participants at time points specified in the SoA (Section 1.3). Total ribonucleic acid will be isolated and used for differential gene expression analyses to better understand the pathologic mechanisms involved in AD and to potentially identify a treatment response signature to bermekimab.

Stopping Analysis

Biomarker analyses are dependent upon the availability of appropriate biomarker assays and clinical response rates. Biomarker analysis may be deferred or not performed, if during or at the end of the study, it becomes clear that the analysis will not have sufficient scientific value for biomarker evaluation, or if there are not enough samples or responders to allow for adequate biomarker evaluation. In the event the study is terminated early or shows poor clinical efficacy, completion of biomarker assessments is based on justification and intended utility of the data.

8.7. Medical Resource Utilization and Health Economics

Health Economics parameters are not evaluated in this study.

9. STATISTICAL CONSIDERATIONS

Statistical analysis will be done by the sponsor or under the authority of the sponsor. A general description of the statistical methods to be used to analyze the efficacy and safety data is outlined below. Specific details will be provided in the SAP.

9.1. Statistical Hypotheses

The hypothesis for this study is that at least 1 of the test doses/dosages IV bermekimab treatment is superior to placebo as assessed by the proportion of participants with an EASI-75 ($\geq 75\%$ improvement from baseline) at Week 16.

9.2. Sample Size Determination

This study is designed to enroll approximately 60 participants in order to have sufficient power to detect a difference between the participants receiving bermekimab and the participants receiving placebo for the primary endpoint of the proportion of participants achieving EASI-75 at Week 16.

The EASI-75 response rate in the bermekimab 400 mg qw group was approximately 70% at Week 7 from the open label study (2018-PT044 [[NCT03496974](#)]). The EASI-75 response rates in placebo group at Week 16 were 15% and 12%, in the 2 Phase 3 trials of dupilumab vs placebo in the treatment of adult participants with moderate-to-severe AD ([Simpson 2016](#)).

The EASI-75 response at Week 16 is assumed to be 15% for placebo, and 65% to 70% for the bermekimab treatment population ([Table 3](#)). Based on these assumptions, approximately 60 participants (10 in Part A, 30 in Part B, and 20 in Part C) are planned to be randomized. In each Part, participants will be randomized in a 4:1 ratio to bermekimab or placebo. Thus, there will be 8 participants in the bermekimab 800 mg group, 24 participants in the bermekimab 1200 mg group, 16 participants in the bermekimab C dose, and 12 participants total across the placebo groups.

These sample sizes provide the study with at least 80% power to detect a treatment difference between the each bermekimab treatment group and the pooled placebo treatment group in EASI-75 at Week 16 based on a Fisher's Exact test at a Type I error rate of 0.1 (2-sided).

Table 3: Power to detect a treatment difference in EASI-75 at Week 16*

Placebo	Bermekimab	Difference	Power
Bermekimab 1200 mg (n=24) vs placebo (n=12)			
15%	65%	50%	85%
15%	70%	55%	92%
12%	60%	48%	83%
12%	65%	53%	90%
12%	70%	58%	96%
Bermekimab dose C (n=16) vs placebo (n=12)			
15%	70%	55%	86%
15%	75%	60%	92%
12%	65%	53%	83%
12%	70%	58%	91%

EASI Eczema Area and Severity Index.
*Power is not calculated for Part A due to small sample size.

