Results from a Phase 2, open label, dose escalation study of bermekimab in participants with moderate-to-severe atopic dermatitis showed that bermekimab appeared to be safe, well tolerated, and active at reducing the severity of atopic dermatitis, including reducing itch and pain (study 2018-PT044, [NCT03496974](#)). Thirty-eight patients across 9 clinical sites in 2 treatment groups received 1 of 2 SC doses: a low (200 mg, n = 10) or high (400 mg, n = 28) dose of bermekimab once weekly for either a 4- or 8-week treatment regimen, respectively. Safety was assessed by pre- and post-treatment measurements of vital signs, clinical laboratory assessments (blood chemistry,

urinalysis, and hematology), allergic reaction monitoring, and adverse event monitoring. Efficacy was assessed by change in Eczema Area and Severity Index (EASI), Investigator Global Assessment (IGA), Numerical Rating Scale, Severity Scoring of Atopic Dermatitis (SCORAD), Patient-Oriented Eczema Measure (POEM), Dermatological Life Quality Index (DLQI), and Global Individual Signs Score from baseline to visit 9. The primary measure of efficacy was the EASI. In the study, 39% of participants in the 400 mg dose group achieved a $\geq 75\%$ improvement in EASI score (EASI-75) after 4 weeks of therapy and 71% achieved EASI-75 at Week 7. An IGA score of 0 (clear) or 1 (minimal) and a ≥ 2 -point decrease from baseline IGA at Week 7 was achieved by 25% of participants in the 400 mg dose group. In addition, 61% of participants in the 400 mg dose group achieved a 4-point or greater improvement in the Pruritus Numerical Rating Scale for overall itch; and 75% achieved a 4-point or greater improvement by Week 8. Furthermore, 80% of participants in the 400 mg dose group achieved a 4-point or greater improvement in the Numerical Rating Scale for pain by Week 8.

Preliminary internal company data from a Phase 2 study, 77474462ADM2002 ([NCT04021862](#)), have recently become available and were used to support decisions about the dose regimens and design of this study. Study 77474462ADM2002 is a double-blind, placebo-controlled study of bermekimab in adult participants with moderate-to-severe AD. The primary endpoint of this study is the percentage of patients achieving EASI-75 at Week 16. Preliminary results from this study are discussed in Section 4.3. Justification for Dose.

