4.3. Justification for Dose

In this study, bermekimab dose regimens of 800 and 1200 mg IV qw will be evaluated in Parts A and B, respectively. Following the interim analysis, and for the purpose of analyzing target coverage at a higher dose of bermekimab in this population, a bermekimab dose regimen of up to 2400 mg IV qw (Part C) may be evaluated. These dose regimens were chosen to build upon the bermekimab PK, efficacy and safety data from a Phase 2 placebo-controlled study in participants with AD (77474462ADM2002, [NCT04021862](#)), a Phase 1 open-label study in healthy volunteers (77474462ADM1001, [NCT04544813](#)), and a Phase 2 placebo-controlled study in participants with HS ([Kanni 2018](#), [NCT02643654](#)). Additionally, safety margins derived from predicted human exposure and the exposure observed during preclinical toxicity studies in cynomolgus monkeys were also considered in selection of the dose regimens.

The Week 16 data from study 77474462ADM2002 ([NCT04021862](#)) in patients with AD showed significant effect of bermekimab 400 mg SC qw group relative to placebo (EASI-75: 34.5% vs 13.8%, respectively), while the 400 mg SC once every 2 weeks (q2w) group showed numerically higher EASI-75 response relative to placebo (EASI-75: 24.1% vs 13.8%, respectively). The dose-response observed between 400 mg SC qw and 400 mg SC q2w (EASI-75: 34.5% vs 24.1%) warranted additional dose-ranging studies in order to expand the dose range to explore target engagement in skin tissue and maximize efficacy in AD. A Phase 2 placebo-controlled study (77474462ADM2001) is being conducted with SC administration of bermekimab at doses of 350 and 700 mg qw.

In this current Phase 2 study, IV infusion will be utilized in order to further expand the dose range potentially up to 2400 mg qw. The dose regimens of 800, 1200 and 2400 mg IV qw are predicted to provide 1.9-, 2.9- and 5.7-fold higher exposure (AUC) at steady-state compared to 700 mg SC qw (assuming 60% bioavailability), respectively. Overall, the IV doses proposed in this current study is expected to maximize the target coverage in the skin tissue and potentially contribute to improved efficacy in AD.

The weekly dosing frequency was selected based on bermekimab half-life ($t_{1/2}$). Bermekimab $t_{1/2}$ was estimated to be approximately 1 week necessitating weekly dosing to maintain adequate drug exposure over the entire dosing interval.

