The study would be considered as positive if any of the comparisons for primary endpoint analysis (bermekimab 1200 mg vs placebo, and bermekimab C dose vs placebo) is less than or equal to p-value of 0.1. No formal statistical testing will be performed for the 800 mg vs placebo. For the analyses described above, participants with ICEs 1 through 3 before Week 16 will be considered as EASI-75 nonresponders at Week 16. For participants with ICE 4, observed data after this ICE will be utilized in the analysis. In addition, participants who do not return for evaluation or have missing components of EASI will also be considered as nonresponders at Week 16.

To examine the robustness of the primary endpoint analysis, additional analyses of the primary endpoint will be conducted using different data handling approaches; these analyses will be described in the SAP. To evaluate the consistency of the efficacy, subgroup analysis of the primary endpoint will be performed.

No adjustment for multiple comparisons will be made for primary endpoints.

Secondary Endpoints

The secondary analyses pertaining to efficacy are:

- The proportion of participants with both vIGA-AD 0 or 1 (on a 5-point scale) and a reduction from baseline of ≥ 2 points at Week 16 will be compared between each of the bermekimab groups and the placebo group.
- Proportion of participants with improvement (reduction) of eczema-related itch NRS ≥ 4 from baseline to Week 16 among participants with a baseline itch value ≥ 4 will be compared between each of the bermekimab groups and the placebo group.
- The proportion of participants with EASI-90 response at Week 16 will be compared between each of the bermekimab groups and the placebo group.

No adjustments for multiple comparisons will be made for the secondary endpoints.

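### The claim of at least 80% power for each bermekimab group is not met by the 800 mg group (56% to 74% at the assumed rates) and is borderline for Dose C at the plan's own lower response rate

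*Protocol*

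**What the plan says.** Protocol 9.2 lists three active groups (800 mg, n=8; 1200 mg, n=24; Dose C, n=16) and 12 placebo participants pooled across Parts. It then states: "These sample sizes provide the study with at least 80% power to detect a treatment difference between the each bermekimab treatment group" and pooled placebo, using Fisher's exact test at a two-sided Type I error rate of 0.1. The planning rates are: "The EASI-75 response at Week 16 is assumed to be 15% for placebo, and 65% to 70% for the bermekimab treatment population". SAP 3 carries the same statement, rates and table.

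Table 3 (Table 1 in the SAP) covers only two of the three groups. Its footnote reads: "Power is not calculated for Part A due to small sample size". The 1200 mg block includes 65% versus 15%. The Dose C block begins at 70% versus 15%.

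The status of 800 mg varies by place:

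- Protocol 9.4.2, in the paragraph on the primary analysis, applies Fisher's test to every bermekimab group against placebo.
- The next paragraph of 9.4.2 defines a positive study by 1200 mg and Dose C only, and adds: "No formal statistical testing will be performed for the 800 mg vs placebo".
- SAP 2 includes 800 mg in the null hypothesis.

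**The concern.** The sentence comes straight after the three group sizes, so taken at its word it promises 80% power for all three doses. Eight participants against 12 is a very small comparison, and the footnote concedes that its power was never worked out. The sentence and the footnote therefore disagree.

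The missing Dose C row matters for a related reason. It is the one cell that would show whether the claim holds for Dose C at the lower end of the plan's own assumption. Neither document says which form of Fisher's test, or which approximation to it, produced the table, so a reader cannot settle the point from the text.

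At stake is the accuracy of the power statement that both documents give as the justification for the sample size.

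**Working it through.** **Inputs.** Group sizes 8, 24 and 16 against 12; Fisher's exact test, two-sided 0.1; rates 65% to 70% versus 15% (all Protocol 9.2). Table 3 also uses a 12% placebo rate.

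**Methods.** Let p1 and n be the active rate and size, and p0 the placebo rate.

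- A, probability-ordered Fisher: sum Bin(x; n, p1) × Bin(y; 12, p0) over all outcomes (x, y) with two-sided p ≤ 0.10.
- B, tail-doubled Fisher: the same sum over outcomes with one-sided p ≤ 0.05.
- C, continuity-corrected normal approximation: Φ[(p1 − p0 − c − 1.645·SE0)/SE1], where c = ½(1/n + 1/12), SE0 = √[p̄(1 − p̄)(1/n + 1/12)], p̄ = (n·p1 + 12·p0)/(n + 12), and SE1 = √[p1(1 − p1)/n + p0(1 − p0)/12].

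**Step 1: reproduce the printed table.** For 1200 mg at 65% versus 15% by method C: c = 0.0625, p̄ = (15.6 + 1.8)/36 = 0.4833, SE0 = 0.1767, SE1 = 0.1418. Then z = (0.50 − 0.0625 − 0.2906)/0.1418 = 1.036, and power is 85.0% (printed 85%). All nine cells agree:

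| Group | Rates | Printed | C | B | A |
|---|---|---|---|---|---|
| 1200 mg | 65 v 15 | 85 | 85.0 | 85.1 | 90.2 |
| 1200 mg | 70 v 15 | 92 | 92.1 | 91.5 | 94.9 |
| 1200 mg | 60 v 12 | 83 | 82.6 | 83.5 | 88.7 |
| 1200 mg | 65 v 12 | 90 | 90.5 | 90.3 | 94.0 |
| 1200 mg | 70 v 12 | 96 | 95.7 | 94.9 | 97.1 |
| Dose C | 70 v 15 | 86 | 85.6 | 86.1 | 89.0 |
| Dose C | 75 v 15 | 92 | 92.3 | 91.8 | 93.7 |
| Dose C | 65 v 12 | 83 | 83.3 | 85.3 | 87.7 |
| Dose C | 70 v 12 | 91 | 90.6 | 90.9 | 92.9 |

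Method C matches all nine printed cells to the percent. Method B is within 2.3 points. The 1200 mg group exceeds 80% at both assumed rates by every method.

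**Step 2: 800 mg (8 v 12).** By C at 65% versus 15%: c = 0.1042, p̄ = (5.2 + 1.8)/20 = 0.35, SE0 = 0.2177, SE1 = 0.1976. Then z = (0.50 − 0.1042 − 0.3581)/0.1976 = 0.191, and power is 57.6%.

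| Rates | A | B | C |
|---|---|---|---|
| 65 v 15 | 65% | 56% | 58% |
| 70 v 15 | 74% | 66% | 67% |
| 65 v 12 | 71% | 63% | 65% |
| 70 v 12 | 79% | 72% | 73% |

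No cell reaches 80%. With 15% placebo, 80% power needs a true response of 73.9% (A), 77.8% (B) or 77.4% (C), all above the assumed range.

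**Step 3: the missing Dose C row (16 v 12, 65% versus 15%).** By C: c = 0.0729, p̄ = (10.4 + 1.8)/28 = 0.4357, SE0 = 0.1894, SE1 = 0.1576. Then z = (0.50 − 0.0729 − 0.3115)/0.1576 = 0.73, and power is 76.8%. By B it is 78.9%, and by A 82.3%.

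**Step 4: response needed for 80% power with 15% placebo.** 1200 mg: 58.2% (A), 61.9% (B), 62.3% (C). Dose C: 63.5%, 65.7%, 66.7%. Rounded up, so that power is at least 80%, these are 59, 62 and 63% for 1200 mg and 64, 66 and 67% for Dose C.

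**The case against.** **800 mg was never meant to be powered.** The footnote, the absence of an 800 mg block and the no-test statement all show this, and a careful reader would discount the word each. That is fair as to intent. But these passages contradict the sentence without correcting it. SAP 3 repeats it, and SAP 2 still puts 800 mg in the null hypothesis.

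**An uncorrected chi-square calculation does pass 80% for 800 mg at 70% versus 15% (84%).** It gives 77% at 65%. It is not the stated test, and it gives 94% where Table 3 prints 85%, so it is not the table's method.

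**The Dose C claim is correct for the test as named.** The usual two-sided Fisher test gives 82.3%. This stands, and it is why a reader who infers that the claim is false for Dose C goes too far. The gap is one of presentation: by the method that matches the printed table, the omitted row would show 77%.

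**The study needs only one win.** Under 9.4.2 it is positive if either 1200 mg or Dose C succeeds. With both at 65% and a shared 15% placebo group, the chance of at least one win is about 95% (A) or 92% (B). So a reader should not infer that 60 participants is too few on the sponsor's assumptions. The sentence, however, claims power for each group, not for the study.

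**The assumed rate.** A reader might also infer that 65% to 70% is refuted by the randomized Week 16 result in Protocol 4.3, which "showed significant effect of bermekimab 400 mg SC qw group relative to placebo (EASI-75: 34.5% vs 13.8%, respectively"). The documents do not support that. The 400 mg regimen gives lower exposure: at the protocol's 60% bioavailability it delivers 240 mg, so 1200 mg IV is 5.0 times as much if exposure is dose-proportional. Section 4.3 discloses the result and argues for better efficacy at higher exposure. What stands is smaller: 9.2 cites only the open-label source ("The EASI-75 response rate in the bermekimab 400 mg qw group was approximately 70% at Week 7 from the open label study"), although 2.2 says the randomized data "have recently become available and were used to support decisions about the dose regimens and design of this study".

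**Conclusion.** The power statement is wrong as written for 800 mg: 56% to 74% at the assumed rates with 15% placebo, and at most 79% with 12%. For Dose C it is borderline at 65% versus 15% (77% to 82%, depending on a method that neither document names). It holds for 1200 mg, and all nine printed cells reproduce.

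These figures assume the planned group sizes, independent binomial responses and full pooling of the 12 placebo participants.

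The consequence is limited. SAP 1 and SAP 5.3.2 say that the study ended early and that no formal analyses will be done. No test result depends on this, but both documents still give the figure as the basis for the sample size.

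**What to change.** In both Protocol 9.2 and SAP 3:

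1. Limit the power sentence to 1200 mg and Dose C, name the calculation method, and state that no power is claimed for 800 mg. If response thresholds for 80% power at 15% placebo are given, use the pair for the named method, rounded up (1200 mg, then Dose C): probability-ordered Fisher 59% and 64%; tail-doubled Fisher 62% and 66%; continuity-corrected approximation 63% and 67%.
2. Add the Dose C row at 65% versus 15% by that method (82%, 79% or 77%, in the same order). If it is below 80%, say that Dose C reaches 80% only above a 65% response.

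Across the documents:

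3. Reconcile the status of 800 mg between SAP 2 (in the null hypothesis), the primary analysis paragraph of Protocol 9.4.2 (every bermekimab group compared) and the next paragraph of 9.4.2 (no formal test).
4. Optionally, cross-refer to the randomized Week 16 result in Protocol 4.3 (34.5% versus 13.8%, at lower exposure) beside the open-label Week 7 rate. Extra table rows at lower response rates are not required.

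The cost is one rewritten sentence, a method label and one table row in each document, plus the wording on 800 mg. The test, alpha, sample size and printed cells do not change.
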